9.2.2.3 Actual Treatment

For each type of lesion, the primary analysis will be performed using the actual treatment rather than the planned treatment. If a subject receives both treatments, then the treatment that the subject received for the longest period is used as the actual treatment for this sensitivity analysis.

9.2.2.4 Including Small Lesions at Baseline

For each type of lesion, the primary analysis performed on a redefined outcome. The outcome will be the change from baseline to end-of-treatment in the sum of all lesions of that type including the lesions below <10 mm in size at baseline, as opposed to the primary analysis focusing on all lesion of that type that are ≥ 10 mm at baseline.

9.2.2.5 Adjusting for Previous Hormonal Treatment

For each type of lesion the primary analysis will be performed adjusting for previous hormonal treatment as a fixed factor. Previous hormonal treatment will be defined as a Yes/No variable and will take the value yes if the subject has any prior medication with a stop date less than 6 month prior to first use of IMP, with ATC classification 1st level equal to “Genito urinary system and sex hormones” and ATC classification 2nd level equal to “sex hormones and modulators of the genital system” or “other gynaecologicals” and the value no otherwise.

9.2.3 Additional Analyses

Based on the endometriosis FAS (endometrioma and DIE). The changes from baseline to end-of-treatment in the sum of sizes (mm) of all endometriosis (endometrioma and DIE) lesions ≥ 10 mm at baseline will be analysed using a similar ANCOVA model and a similar imputation scheme as the primary analysis.

9.2.4 Figures

Figures based on the FAS for each of the three types of lesion (endometrioma, DIE and adenomyosis), for endometriosis (endometrioma and DIE), and for the three types of lesions combined will be prepared. The mean of the primary outcome (with 95% confidence interval) will be graphed as a function time (Baseline and End-of-treatment) for the two treatment groups in the same figure. No imputations will be used for the figures.

9.3 Secondary and Exploratory Endpoints

The summaries and analysis of the secondary efficacy endpoints will be performed for the FAS. No sensitivity analysis will be performed for any of the secondary or exploratory outcomes.

9.3.1 Percentage of Lesion Size Changes by Type on MRI

For each type of lesion (endometrioma, DIE and adenomyosis), the percentage change in the sum of lesion sizes, will be analysed using a similar ANCOVA model and a similar imputation scheme as the primary endpoint, but both the baseline sum of sizes and the cycle 4 / end-of-treatment sum of sizes will be log transformed prior to analysis. The estimated difference between treatment groups will be back transformed to ease interpretation.

If the end-of-treatment MRI examination results in that all lesions of the same type are assessed as truly not detectable the sum will be imputed as 1 mm, in order to facilitate the log-transformation.

9.3.2 Endometrioma and DIE Changes in Volume on MRI

The absolute sum of volumes at baseline and at end-of-treatment, and the change in the sum of volumes from baseline to end-of-treatment will be summarised. The summaries will be performed by treatment and in total for each of the two types of lesions (endometrioma and for the two types combined and DIE).

For each of the two types of lesions (endometrioma and DIE) and for the two types combined, the change in the sum of lesion volumes, will be analysed using a similar ANCOVA model and a similar imputation scheme as the primary endpoint.

9.3.3 Endometrioma Size Changes by TVU

The absolute sum of sizes of endometrioma lesions assessed by TVU at baseline and at end-of-treatment, and the change in the sum of sizes from baseline to end-of-treatment will be summarised. The summaries will be performed by treatment and in total only for endometrioma lesions.

The change in the sum of lesion sizes assessed by TVU, will be analysed using a similar ANCOVA model and a similar imputation scheme as in the primary endpoint.

9.3.4 Other Secondary and Exploratory Endpoints

All summaries in this section will be performed by treatment and in total. As indicated in [Table 9-1](#) some endpoints will be summarised and analysed for each of the three types of lesion (endometrioma, DIE and adenomyosis) and for endometriosis (endometrioma and DIE), some for all types of lesion combined, and some for both.

No imputation will be done for the analysis of these other secondary and exploratory endpoints. The endpoint derived from the MRI will, however, use the end-of-treatment assessment even if the end-of-treatment assessment is performed before end of cycle 4.

Table 9-1 Analyses of Other Secondary and Exploratory Endpoints

Endpoint	Analysis method					Presentation	
	ANCOVA	Repeated measures ANCOVA	Logistic regression	Negative Binomial regression	Proportional odds	By type of lesion and disease	All types of lesions combined
Proportion of lesions by type with a decrease in a size of ≥ 5 mm on MR images at cycle 4			X			X	
Proportion of subjects with a lesion of any type decreased in a size of ≥ 5 mm on MR images at cycle 4			X				X
Number of new endometrioma, DIE and adenomyosis lesions by type on MR images at cycle 4				X		X	
Number of disappearing endometrioma, DIE and adenomyosis lesions by type on MR images at cycle 4				X		X	
Changes in the total physical sign pain score and change in the total symptom and sign severity score of the Biberoglu and Behrman (B&B) scale at cycle 4	X					X	X
Changes in the Numerical Rating Scale (NRS) pain scores at cycles 1, 2, 3 and 4		X				X	X
Changes in each of the five EHP-30 scores and the total EHP-30 score per cycle at cycles 2 and 4		X				X	X
Changes in the menstrual bleeding pattern over 4 cycles		X			X	X	X
Change in serum levels of prolactin, TSH, IGF-1 during cycle 1, at cycles 2 and 4		X				X	X
Changes in the sizes of uterine fibroids on MR images at cycle 4	X						
Changes in the sizes of uterine fibroids assessed by TVU at cycle 4	X						
Changes in circulating levels of VEGF, PIGF, IL-6, CA125 and sFlt-1 at cycle 4	X					X	X

Note: Exploratory endpoints are shaded in grey.

9.3.4.1 Binary Endpoints

Secondary endpoints related to proportion of lesions with a decrease in a size of ≥ 5 mm at cycle 4 and proportion of subjects with a lesion of any type that decreased in a size of ≥ 5 mm at cycle 4 will be based on all lesions ≥ 10 mm at baseline.

The proportion of lesions with a decrease as defined above and the proportions of subjects with at least one lesion decreased as defined above will be summarised

The proportion of lesions will be analysed using logistic regression for binary data with logit link function, the generalised estimating equation (GEE) approach will be used to account for correlated data (multiple lesions in one subject), and the analysis will be adjusted for baseline lesion size. The analyses will be performed for each of the three types of lesions, and for endometriosis (endometrioma and DIE).

The proportion of subjects will be analysed using logistic regression for binary data with logit link function, and the analysis will be adjusted for the number of lesions ≥ 10 mm at baseline. The analyses will be performed for the three types of lesions combined.

Menstrual bleeding pattern will be analysed by looking at the first occurrence of change from baseline (visit 2) in the amount of menstrual flow (either to a more heavy flow or to a more mild flow). This will be analysed using the proportional odds regression model. The analyses will be performed for each of the three types of lesions, and for endometriosis (endometrioma and DIE).

The treatment differences between active treatment versus placebo will be reported as odds ratios with 95% confidence intervals and corresponding p-values for each of these endpoints.

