Eligible subjects must have at least one of the following three types of lesions with the following sizes identified by MRI: endometrioma (≥ 20 mm), DIE (≥ 15 mm), and/or adenomyosis (maximum junctional zone thickness ≥ 12 mm or focal lesion ≥ 15 mm). If a subject has more than one type of lesions, she will be grouped under the more rare type in the ranking of DIE, adenomyosis and endometrioma. For example, a subject with both DIE and endometrioma will be included in the DIE sub-group but both types of lesions should be measured. Every measurable lesion (defined as ≥ 10 mm in size) of any type should be recorded and should be summed up by type for primary analysis. For DIE and endometrioma, lesions will be measured both in size and in volume. For uterine fibroid, only size will be measured. Size will be recorded in mm as the longest diameter in the plane of measurement. Volume will be recorded in mm^3 using a semi-automated method based on 3D region-growing algorithm, adjusted with manual correction. For adenomyosis, the maximum junctional zone thickness (applicable to diffuse adenomyosis) or the size of the largest focal lesion (applicable to focal adenomyosis) will be measured. All MRIs should be uploaded into a specific image repository allocated for this trial within 2 business days for central reading and analyses by a specialised imaging laboratory. Subject eligibility with regard to inclusion criterion no. 6 must be determined based on the central MRI reading report.

Subjects are required to fast for 3-4 hours before the MRI examination. The preparations for MRI examination should follow the trial-specific MRI manual. The MRI procedures will include the following main sequences:

- Fast spin echo – T2-weighted images (FSE-T2)
- Diffusion weighted (DW-IVIM) images with more than 2 b-values
- Gradient echo (GRE) – T1-weighted images with varying flip angles (GRE-T1-VFA)
- Dynamic, contrast-enhanced, spoiled GRE T1-weighted images (DCE-PKM-Gd)
- Late gadolinium enhancement spoiled GRE T1-weighted images (GRE-T1-LATEGd)

Other details for the MRI examination will be specified in the MRI manual. Prior to the start of the trial, site radiologists will be trained on the MRI manual. Site radiologists must follow the MRI manual for the preparation and the execution of the MRI assessment.

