3.3 Determination of Sample Size

The sample size calculation is based on demonstrating superiority of quinagolide vaginal ring compared to placebo vaginal ring on the primary endpoint of changes in the sizes of endometrioma, DIE and adenomyosis lesions summed by type on MRI at cycle 4. An important assumption behind the sample size calculation is an equal magnitude of treatment effect for all three types of lesions. For example, for adenomyosis, by assuming an average baseline lesion size of 18 mm and a standard deviation of 4.5 mm [1], a sample size of 24 randomised subjects (16 on active treatment and 8 on placebo) will have 83% power to detect a treatment effect difference of 6 mm (corresponding to a 33% reduction in lesion size) using a two-sample t-test at a 5% two-sided significance level. A similar assumption, i.e. the ratio between treatment effect and standard deviation is 4 to 3, is made for DIE and endometrioma to conclude 24 subjects to be randomised per sub-group. In total, 72 subjects will be randomised in this trial.

Table 3-2 Sample Size by Treatment Effect Difference

Difference in the sum of lesion size reduction between quinagolide vaginal ring group and placebo vaginal ring group		Number of subjects in total ^a	
Absolute difference (mm)	Relative difference ^b (%)	Power 80%	Power 90%
4.5	25	39	51
5.0	28	33	42
5.5	31	27	36
6.0	33	24	30
6.5	36	21	27
7.0	39	18	24
7.5	42	15	21

a Using a 2:1 randomisation and assuming a standard deviation of 4.5 mm.

b Assuming an average baseline lesion size of 18 mm.

If the drop-out rate in any of the sub-groups are larger than 10%, the sample size of randomised subjects for that sub-group may be increased to up to 30.

The study was planned to be have a randomisation ratio of 2:1 with 2 subjects receiving quinagolide vaginal ring for each subject receiving placebo vaginal, however it was discovered, after LPLV but before database lock, that the randomisation list used during the study had a 1:1 ratio between quinagolide vaginal ring placebo vaginal ring. The use of a 1:1 ratio instead of a 2:1 ratio will increase the power to detect a difference between quinagolide vaginal ring and placebo vaginal ring.

4 Subject Disposition

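### The subject-level 5 mm responder model adjusts for lesion count but not lesion size; adding the largest baseline size would be a cheap, minor improvement

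*SAP*

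**What the plan says.** SAP 9.3.4.1 (Binary Endpoints) defines two responder endpoints on lesions of at least 10 mm at baseline.

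- **Lesion level.** The proportion of lesions that shrink by at least 5 mm is analysed by GEE logistic regression, separately for each type and for endometriosis. For this model, "the analysis will be adjusted for baseline lesion size".
- **Subject level.** The endpoint is the "proportion of subjects with a lesion of any type that decreased in a size of ≥ 5 mm at cycle 4". It is analysed by ordinary logistic regression, and "the analysis will be adjusted for the number of lesions" of at least 10 mm at baseline. On scope, "The analyses will be performed for the three types of lesions combined".

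Table 9-1 in SAP 9.3.4 marks the subject-level endpoint only under all lesion types combined. Protocol 9.6.3 names logistic regression for both endpoints and lists no covariates, so no size term comes from there. The SAP gives no reason why the two models carry different covariates.

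**The concern.** The cut-off is a fixed number of millimetres applied to lesions of very different sizes. The entry thresholds already differ by type: "endometrioma (≥ 20 mm), DIE (≥ 15 mm), and/or adenomyosis (maximum junctional zone thickness ≥ 12 mm or focal lesion ≥ 15 mm" mm). The plan also states its target effect as a percentage in SAP 3.3, and SAP 9.3.1 analyses percentage change. If lesions shrink roughly in proportion to their size, women with large lesions pass 5 mm more often.

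The primary ANCOVA (SAP 9.2.1), the other continuous endpoints (SAP 9.3.4.3) and the lesion-level responder model all adjust for the baseline measurement. The subject-level responder model does not. It is also the one that pools all three types.

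The design does not clearly prevent a size imbalance. Protocol 4.2.2 names site as the only stratification factor, although Protocol 3.1.2 speaks of randomising within each sub-group. SAP section 12 reports four or fewer subjects at four of six sites. At stake are how far the reported odds ratio depends on a chance difference in lesion size between arms, and a little power.

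**Working it through.** **1. The plan's own figure.** The documents give no power for the responder endpoint. For the primary endpoint, SAP 3.3 works "by assuming an average baseline lesion size of 18 mm and a standard deviation of 4.5 mm" and concludes that 16 versus 8 subjects "will have 83% power to detect a treatment effect difference of 6 mm (corresponding to a 33% reduction in lesion size"). Check: SE = 4.5 × √(1/16 + 1/8) = 1.949; non-centrality = 6/1.949 = 3.08; df 22. The two-sided 5% t-test then has 83.7% power, which agrees with the stated 83%. All 14 cells of Table 3-2 also reproduce.

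**2. The cut-off as a share of size (5/s).** This is 50% at 10 mm, 41.7% at 12 mm, 33.3% at 15 mm, 25% at 20 mm and 12.5% at 40 mm. With a one-third reduction, mean shrinkage is s/3, which reaches 5 mm only from s = 15 mm upward.

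**3. Response probability for one lesion.** P(decrease ≥ 5) = 1 − Φ((5 − m)/σ), where m is the mean decrease (0 on placebo) and σ the SD of the change. The 25% SD equals 4.5/18, so it matches the plan's SD at 18 mm.

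| Baseline size | m = s/3, σ = 4.5 mm: active / placebo | m = s/3, σ = 25% of s: active / placebo | m = 6 mm, σ = 4.5 mm: active / placebo |
|---|---|---|---|
| 12 mm | 0.41 / 0.13 | 0.37 / 0.05 | 0.59 / 0.13 |
| 20 mm | 0.64 / 0.13 | 0.63 / 0.16 | 0.59 / 0.13 |
| 40 mm | 0.97 / 0.13 | 0.80 / 0.31 | 0.59 / 0.13 |

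Placebo response depends on size only when the noise scales with size. Active response depends on size when either the mean change or the noise does. With the same millimetre change and SD at every size, neither arm depends on it.

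**4. Power and type I error by simulation.** There were 36 versus 36 women (the 1:1 list actually used) and 1,500 trials per setting. The following are assumptions, not document figures: median sizes 35, 22 and 18 mm for endometrioma, DIE and adenomyosis; log-SD 0.4; 1 + Poisson(0.7) lesions for the first two types and one for adenomyosis. Rejection rates at two-sided 5%:

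| Setting | Count only | + log largest size | + size and type |
|---|---|---|---|
| No effect, SD 20% of size | 3.8% | 3.9% | 4.7% |
| 15% shrinkage, SD 20% of size | 64.9% | 67.7% | 68.3% |
| 15% shrinkage, SD 4.5 mm | 87.8% | 87.4% | 87.6% |
| 2.7 mm at every size, SD 4.5 mm | 52.8% | 52.7% | 52.6% |

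Two further simulations of the 15% shrinkage setting with proportional noise gave 66% to 70% and 61% to 66%. The three gains (2.8, 4 and 5 points) average about 4. At 33% shrinkage all models lie between about 98% and 100%, and adding size alone changes nothing (for example 99.5% and 99.6%).

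**5. Chance imbalance.** Same assumptions, noise 20% of size, 3,000 trials. The between-arm difference in mean log largest lesion has an SD of about 0.12. In about one trial in six the active arm is more than 1 SD larger. The average difference in those trials is about 1.5 SD = 0.18, and exp(0.18) = 1.20, so lesions are about 20% larger.

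- No effect, active arm more than 1 SD larger: the median odds ratio is 1.23 with count only and 0.96 with size added. A separate simulation gave 1.18 and 0.98.
- 15% shrinkage: with count only, the median odds ratio is 2.9 when active lesions are more than 1 SD smaller and 4.7 when they are more than 1 SD larger (power 45% and 78%). With size added it is 4.4 and 4.5 (power 64% and 70%).

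**The case against.** The planned covariate is sensible. For an endpoint met by any lesion, the count sets how many chances a woman has to respond, and a woman with several lesions has no single baseline size. Size is handled in the primary, percentage-change and lesion-level analyses. Baseline size, sum and type mix are tabulated by treatment (SAP 7.1.4), so an imbalance would be visible. Treatment is randomised, and the ordinary confidence interval already covers chance imbalance. Adding a covariate to a logistic model also changes what is estimated: the median odds ratio moves from 3.8 to 4.5 partly because it becomes conditional on size. The 10 mm example is extreme too, since every eligible woman has a lesion or junctional zone of at least 12, 15 or 20 mm.

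Most of this stands, and it limits the point to a minor one. It does not remove it. Averaged over all randomisations there is no bias, but the trial is run once. Under proportional noise the count-only odds ratio moves with whichever imbalance occurs, and the size term removes most of that movement.

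A reader might go further in three ways that the documents do not support.

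- **That baseline size largely decides who responds in both arms.** This needs noise proportional to size, which is not stated anywhere. With the plan's 4.5 mm SD held constant, single-lesion placebo response is 0.13 at every size.
- **That the lesion sub-group belongs in the main model as well.** In four simulated settings with 15–20% shrinkage, adding it to size moved power from 71.1% to 70.3%, 80.2% to 78.9%, 87.2% to 86.4% and 91.9% to 92.1%, so there is no consistent gain. Sub-group is also a poor proxy for lesion type: it follows a rarity ranking, with reallocation once a group is full (Protocol 7.1.1), whereas the SAP's by-type analyses go by lesions present (SAP 3.2). In the working above, the model with size and type failed to fit in up to 13 of 1,500 simulated trials.
- **That this endpoint uses all 72 women.** Seventy-two is the planned total. SAP 9.3.4 imputes nothing for this endpoint, and an end-of-treatment MRI is planned only for completers and for those who discontinue during or after cycle 2.

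**Conclusion.** The point holds as a minor improvement. The subject-level model leaves out a covariate that its neighbouring model includes, and the SAP does not say why. If shrinkage or noise is roughly proportional to size, the omission lets a chance size imbalance shift the odds ratio and costs up to about 4 points of power. If the millimetre change and SD do not depend on size, it costs nothing, and adding the term costs next to nothing (0.1 points in that setting). These sizes rest on assumed lesion distributions and 20% proportional noise; the documents supply neither.

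The different covariates might be read as an error or as a source of false positives. They are neither: simulated type I error under the planned model is 3.8%, and this is one secondary endpoint outside the Hochberg procedure.

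**What to change.** In SAP 9.3.4.1, add the log of the largest baseline lesion size (among lesions of at least 10 mm) to the subject-level logistic model, beside treatment and number of lesions. Specify it before unblinding. Leave lesion sub-group out of the main model; at most, use it in a supportive one. If the sponsor prefers the count-only model, one sentence saying why size is omitted would do.

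The cost is one line of text and one more coefficient, from data already collected. The odds ratio becomes conditional on baseline size, and the report should say so.

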7.2.5 Menstrual Bleeding Pattern

At each RM+7 visit from randomisation to end-of-treatment / cycle 4, the site staff should inquire about the subject's immediate past menstrual period, including the start and stop dates (if available) of menstrual bleeding and the amount of menstrual flow. The amount of menstrual flow will be graded as none (no bleeding), mild (less than normal flow), moderate (normal flow) and heavy (more than normal flow).

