9.6.3 Secondary Endpoints

The percentage change in the sum of lesion sizes by type, will be analysed using a similar ANCOVA model as the primary endpoint, but both the baseline and the cycle 4 / end-of-treatment results will be log transformed prior to analysis. The estimated difference between treatment groups will be back transformed to ease interpretation.

Secondary endpoints related to proportion of lesions and proportion of subjects with a decrease in a size of ≥ 5 mm at cycle 4 will be based on all lesions ≥ 10 mm at baseline and will be analysed using logistic regression for binary data with logit link function. The generalised estimating equation (GEE) approach will be used to account for correlated data where appropriate.

Count data related to the number of new / disappearing lesions by type, based on all lesions, will be analysed with repeated measures negative-binomial regression using a GEE approach. The regression analysis will be performed with log link function using the appropriate off-set.

Changes from baseline in the volume of endometrioma/DIE lesions assessed by MRI at cycle 4 and in the sizes of endometrioma assessed by TVU at cycle 4 will be analysed similarly to the primary endpoint, but sensitivity analyses will not be performed for these secondary endpoints.

Secondary endpoints related to PROs (B&B, NRS and EHP-30) and endocrine parameters will be analysed using a repeated measures ANCOVA model, with the change from baseline at each post-baseline time point as the dependent variable, the baseline value as a covariate, and the treatment group and treatment by time as fixed effect. The error-covariance matrix will be unstructured.

Changes in the menstrual bleeding pattern will be analysed by investigating the time to first event of change in bleeding pattern using the proportional odds regression model.

Plasma concentration of quinagolide and its metabolites will be analysed descriptively. A population pharmacokinetic modelling method will be outlined in a modelling analysis plan under the responsibility of the Translational Medicine Department of Ferring Pharmaceuticals A/S and the results will be reported separately.

All analyses and respective definitions of the endpoints will be further detailed in the SAP.

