2.2.2 Secondary Endpoints

- Percentage of changes in the sizes of endometrioma, DIE and adenomyosis lesions summed by type on MR images at cycle 4
- Proportion of lesions by type with a decrease in a size of ≥ 5 mm on MR images at cycle 4
- Proportion of subjects with a lesion of any type decreased in a size of ≥ 5 mm on MR images at cycle 4
- Number of new or disappearing endometrioma, DIE and adenomyosis lesions summed by type on MR images at cycle 4
- Changes in the volumes (mm^3) of endometrioma and DIE lesions summed by type on MR images at cycle 4
- Changes in the sizes of endometrioma assessed by TVU at cycle 4
- Changes in the mean individual and total symptom and sign severity of scores of the Biberoglu and Behrman (B&B) scale at cycle 4
- Changes in the Numerical Rating Scale (NRS) pain scores per cycle at cycles 1, 2, 3 and 4
- Changes in the Endometriosis Health Profile-30 (EHP-30) scores at cycles 2 and 4
- Changes in the menstrual bleeding pattern over 4 cycles
- Serum levels of prolactin, thyroid-stimulating hormone (TSH), insulin-like growth factor-1 (IGF-1) during cycle 1, at cycles 2 and 4
- Plasma concentrations of quinagolide and its metabolites during cycles 1 to 4
- Changes in clinical chemistry and haematology parameters and proportion of subjects with markedly abnormal changes
- Frequency and intensity of adverse events

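### The analysis of amount of menstrual flow counts a first change in either direction as one event, so its odds ratio carries no direction and can miss a shift to heavier or lighter flow

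*SAP*

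**What the plan says.** The effect of the ring on menstrual bleeding pattern is a secondary objective, with the endpoint "Changes in the menstrual bleeding pattern over 4 cycles" (SAP section 2.2.2). Protocol section 7.2.5 records one flow grade per cycle on an ordered scale: "graded as none (no bleeding), mild (less than normal flow), moderate (normal flow) and heavy (more than normal flow".

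SAP section 9.3.4.1, under binary endpoints, defines the analysis: "Menstrual bleeding pattern will be analysed by looking at the first occurrence of change from baseline (visit 2) in the amount of menstrual flow", with the qualifier "either to a more heavy flow or to a more mild flow". It continues: "This will be analysed using the proportional odds regression model". The result is an odds ratio with a 95% confidence interval and p-value. The levels of the ordinal response are not given. Protocol section 9.6.3 says the endpoint is "analysed by investigating the time to first event of change in bleeding pattern using the proportional odds regression model", and names no direction.

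Two other places matter. SAP section 9.3.4.3 adds analyses of the number of bleeding days and the cycle length in each treated cycle, plus descriptive tables of delayed or skipped menses. Protocol section 8.3.2 keeps abnormal menstrual bleeding out of adverse event reporting unless it is serious, because the bleeding endpoint is meant to capture it.

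**The concern.** Heavier and lighter flow mean opposite things to a patient, and the scale that is collected distinguishes them. Once both count as the same event, the treatment odds ratio compares how soon flow changes at all. Even a significant result would not say which way flow moved; that follows from the definition and needs no assumed rates.

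The second consequence is loss of sensitivity. If the ring makes lighter flow more frequent and heavier flow less frequent, one component of the event rises and the other falls, and the odds ratio moves towards 1. The comparison is with a single baseline cycle and there are four chances to differ from it, so some women will have the event without any drug effect.

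At stake is the treatment comparison for amount of flow. No other planned model covers it, and non-serious changes in flow are not collected as adverse events.

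**Working it through.** **The plan's own figure.** The documents state no event rate, effect size or power for this endpoint. The only power statement is the primary one (SAP section 3.3): 16 vs 8, difference 6 mm, SD 4.5 mm, 83%. An exact noncentral t calculation gives 83.7%, so it reproduces; it has no bearing on bleeding.

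**Inputs.** From the documents: four treated cycles, two-sided 5% tests, about 24 women per sub-group and 72 in all, and the 1:1 allocation actually used. That gives 12 vs 12 and 36 vs 36. By-type analysis sets can overlap, so 12 vs 12 is indicative. Assumed: the per-cycle chance that the grade is lighter than, the same as, or heavier than at visit 2, with cycles independent and every woman able to move either way.

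**Event without a drug effect.** If any change has chance p per cycle, the event occurs within four cycles with probability 1 − (1 − p)^4:

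- p = 10%: 1 − 0.90^4 = 34%
- p = 20%: 1 − 0.80^4 = 59%
- p = 30%: 1 − 0.70^4 = 76%

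**What merging does.** Take lighter/same/heavier of 15/70/15% on placebo and 30/65/5% on active.

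- Any change: 1 − 0.70^4 = 76% on placebo, 1 − 0.65^4 = 82% on active. The odds ratio for ever against never is (0.8215/0.1785)/(0.7599/0.2401) = 1.45.
- Direction of first change splits those totals in the ratio of the rates. Placebo: 38% lighter, 24% no change, 38% heavier. Active: 0.8215 × 30/35 = 70% lighter, 18% no change, 0.8215 × 5/35 = 12% heavier. The odds ratio for first change being lighter is (0.704/0.296)/(0.380/0.620) = 3.9.
- If the shifts offset exactly (25/70/5% on active), any change is 76% in both arms and the odds ratio is 1.

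**Power.** Simulation, using the tie-corrected Wilcoxon test (the score test of a proportional odds model). Placebo is 15/70/15% throughout, and each cell gives 12 vs 12, then 36 vs 36. Rejection under no effect is about 5% for each test.

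| Active, lighter/same/heavier (%) | Merged event | Direction of first change | First lighter change |
|---|---|---|---|
| 30/65/5 | 7%, 9% | 40%, 86% | about 30%, 72% |
| 25/70/5 (exact offset) | 5%, 5% | 30%, 72% | 16%, 42% |
| 26/66/8 (lighter odds ×2, heavier ×0.5) | 6%, 9% | 22%, 57% | 19%, 49% |
| 31/54/15 (lighter odds ×2.5 only) | 18%, 48% | 15%, 35% | 31%, 74% |
| 26/48/26 (both odds ×2) | 30%, 73% | 5%, 5% | 20%, 49% |

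First lighter change depends only on the lighter rates. Its entry in the top row is therefore taken from scenarios with the same or nearly the same lighter rate: 72% from 30/55/15, and about 30% from the 31/54/15 row. Repeat runs of the top row gave 6% to 7% for the merged event at 12 vs 12 and 9% to 11% at 36 vs 36.

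**The case against.** **A non-directional question is legitimate.** The objective concerns bleeding pattern, not reduction of flow, and Protocol section 1.3 reports no modification of the menstrual cycle in phase 1. Asking whether flow changes at all suits that background, and the last row of the table shows the merged event doing best when flow is disturbed both ways. This stands as a reason to keep the merged event, but not as a reason to report nothing directional.

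**Bleeding is examined elsewhere.** This stands. A reader might infer that the bleeding objective cannot be answered at all. The documents do not support that: bleeding days and cycle length are analysed with sign in SAP section 9.3.4.3, skipped menses are tabulated, and SAP section 9.1 calls for descriptive summaries by treatment. What remains uncovered is a directional treatment comparison for amount of flow.

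**The response may have been meant as lighter / unchanged / heavier.** The SAP does not exclude this, and it would keep direction. The protocol's wording, "time to first event of change in bleeding pattern using the proportional odds regression model", points the other way. If direction was intended, the SAP needs to say so.

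**The rates are invented.** They are assumptions, and they matter. A reader might infer that most women will change grade by chance; at 10% per cycle only 34% do. With placebo 5/90/5% and active 20/77/3%, the merged event has 73% power at 36 vs 36.

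**The comparator must be fair.** A signed score averaged over all four cycles gives about 56% at 12 vs 12 in the first scenario, but part of that gain comes from using more data. Direction of first change (40%) isolates the loss from merging. Independent cycles also flatter the signed score: with within-woman correlation (latent 0.6) it falls to 28%, against 6% for the merged event.

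**Conclusion.** The point holds for amount of flow. Under the natural reading of the two documents, the planned odds ratio cannot distinguish heavier from lighter flow, and opposing shifts move it towards 1. Under the assumed 15/70/15% against 30/65/5%, power is about 7% against 40% at 12 vs 12 and about 9% against 86% at 36 vs 36. These figures rest on assumed rates and independent cycles; smaller opposing shifts give the same ordering with a narrower gap.

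A reader might go further and infer that the merged event hides any drug effect. It does not. Cancellation is complete only when the two shifts offset exactly. A lighter-only effect keeps 48% power at 36 vs 36, against 74% for first lighter change, and a two-way disturbance is detected better by the merged event than by either alternative in the table.

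This is one component of a secondary endpoint with no stated power, outside the Hochberg family. The primary conclusion is unaffected. The change is worth making because it is cheap and makes the result interpretable.

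**What to change.** Before unblinding, amend SAP section 9.3.4.1 to:

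1. State the levels of the ordinal response, for example cycle 1, 2, 3, 4 or no change.
2. Analyse time to first heavier change and time to first lighter change from visit 2 as two separate outcomes, each with its own odds ratio and confidence interval.
3. Keep the merged event as a supplement, described as a test of any change in flow.
4. Optionally, add a repeated-measures ordinal model of the flow grade at cycles 1 to 4, adjusted for the visit 2 grade. This uses all four cycles and allows for women who start at the end of the scale.

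The flow grade is already collected at randomisation and at each RM+7 visit, so the cost is SAP wording and programming. The statistical price is one extra comparison on a secondary endpoint, and lower power than the merged event if flow changes in both directions (49% for first lighter change against 73% in the last row of the table at 36 vs 36). Keeping the merged event as a supplement covers that case.
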